10.5 Compensation for injury

The sponsor/investigator has a liability insurance, which is in accordance with article 7 of the WMO. The sponsor (also) has an insurance, which is in accordance with the legal requirements in the Netherlands (Article 7 WMO). This insurance provides cover for damage to research participants through injury or death caused by the study.

- € 650.000,-- (i.e. six hundred and fifty thousand Euro) for death or injury for each subject who participates in the Research;
- € 5.000.000,-- (i.e. five million Euro) for death or injury for all participants who participate in the Research;
- € 7.500.000,-- (i.e. seven million five hundred thousand Euro) for the total damage incurred by the organisation for all damage disclosed by scientific research for the

Sponsor as 'verrichter' in the meaning of said Act in each year of insurance coverage.

The insurance applies to the damage that becomes apparent during the study or within 4 years after the end of the study.

10.6 Incentives (if applicable)

In compensation for participation, participants will receive a financial compensation of 60 EURO in case of completing the study. Furthermore, travel expenses will be compensated. Proportional amounts will be given in case of incomplete participation. Participants will not receive payment if they only complete the screening visit, but will receive a compensation for travel expenses (if applicable). The screening visit does, however, include a general health check, which would provide beneficial information for the participant. People who started a one week gluten-free diet for the study, will be given an additional 15 EURO compensation to buy some gluten-free products.

11. ADMINISTRATIVE ASPECTS, MONITORING AND PUBLICATION

11.1 Handling and storage of data and documents

Data will be handled confidentially (coded) and the privacy of the participants will be guaranteed, according to the Dutch Personal Data Protection Act ("Algemene Verordening Gegevensbescherming" (AVG)). All electronic Case Report Forms (eCRFs in e.g. Castor) will be coded in such a way that no personal information about the participant can be derived.

All samples and data will be coded in such a way that no personal information about the participant can be derived. Each participant will be allocated to an individual code, which is preceded by an abbreviation to identify the inclusion site:

- Maastricht University Medical Center+: MUMC.S00xx
- Amsterdam UMC location VUmc: VUMC.S00xx
- Wageningen University & Research: WUR.S00xx

These individual codes will be visible on biological samples. Furthermore, the label of each blood sample will contain the date of collection. The principal investigator will keep the key of the code in a locked cabinet, to which only the principle investigator and a co-worker has access. Together with the members of the project team, assigned monitors from the CTCM, IGZ and members of the medical ethical committee will have access to the research data. All primary documents and data shall be kept for 15 years after the end of the experimental phase of the study for possible inspection. The electronic CRF, electronic diary and electronic questionnaires will be developed taking into account current regulations.

In the informed consent, participants indicate whether they give consent for collecting human material (*i.e.* blood samples) that will be used for exclusion of coeliac disease. These blood samples will be drawn by the research physician of this project. All samples will be coded in such a way that no personal information about the participant can be derived. The analysis of the coded blood samples will be carried out by Medische Laboratoria [name] & Collegae. The analyzed blood samples will be destroyed immediately after analysis.

Subjects recruited via Link2Trials can voluntarily give permission to the website to save their contact details for further recruitment for other research by giving consent to data the storage according to the privacy statement listed on web page https://www.proefpersonen.nl/privacy-statement.html. If they do not consent, their data will be deleted after completion of the recruitment for the WoW study. Link2Trials adheres to the AVG.

11.2 Monitoring and Quality Assurance

A qualified monitor of the CTCM will monitor the conduct of the study. A specific monitoring plan will be created after classification of the risk of this study in line with local guidelines.

11.3 Amendments

Amendments are changes made to the research after a favourable opinion by the accredited METC has been given. All amendments will be notified to the METC that gave a favourable opinion.

11.4 Annual progress report

The sponsor/investigator will submit a summary of the progress of the trial to the accredited METC once a year. Information will be provided on the date of inclusion of the first subject, numbers of participants included and numbers of participants that have completed the trial, serious adverse events/ serious adverse reactions, other problems, and amendments.

11.5 Temporary halt and (premature) end of study report

The investigator/sponsor will notify the accredited METC of the end of the study within a period of 8 weeks. The end of the study is defined as when the last participant has completed the end of day questionnaire on day 3. The sponsor will notify the METC immediately of a temporary halt of the study, including the reason of such an action. In case the study is ended prematurely, the sponsor will notify the accredited METC within 15 days, including the reasons for the premature termination.

Within one year after the end of the study, the investigator/sponsor will submit a final study report with the results of the study, including any publications/abstracts of the study, to the accredited METC.

11.6 Public disclosure and publication policy

Publication policy is in agreement with the Centrale Commissie Mensgebonden Onderzoek (CCMO-statement publicatie beleid, 2002) publication statement. The results of the study will be published in peer-reviewed scientific journals. Both positive and negative results of the study will be disclosed. The authorship of the article shall be determined in appropriate consultation based on a considerable contribution to the set-up and execution of the study and an active participation in publication. This study will be registered in a public trial registry before the first volunteer is recruited.

12. STRUCTURED RISK ANALYSIS

12.1 Potential issues of concern

a. Level of knowledge about mechanism of action

The "Expectancy Theory", proposed in the context of social learning, is a mixture of learning and subjective mental—neural processes (32). The theory explains behaviour through individuals' expectancies of the rewarding effects of their action toward a desired outcome.

Therefore, information shapes the beliefs and, thereby, the actions of individuals. Beliefs trigger neurological activities (33) similar to psychoactive agents. Positive beliefs can induce placebo effects, negative beliefs result in debilitating nocebo effects. Furthermore, the bidirectional communication between the brain and the gut axis, is known to contribute to GI symptom development and perception, as involved for example in the pathophysiology of irritable bowel syndrome (34). Thereby, the interplay between gluten and expectation, may elicit a wide array of both intestinal and extra-intestinal symptoms in individuals with NCGS.

b. Previous exposure of human beings with the test product(s) and/or products with a similar biological mechanism

The study breads are commercially available. Bread itself is a harmless food product which is widely consumed daily by the general population worldwide. Oats and oat-based products are well recognised among consumers, due to their good nutritional properties. Oats are widely consumed by people suffering from gluten intolerance and non-coeliac gluten sensitivity. Furthermore, the study of Catassi *et al.* (2013) showed that the consumption of gluten by non-coeliac gluten sensitive participants does not lead to coeliac-specific antibodies and villous atrophy or any allergy related symptoms. In this study, the provided study breads contain no more gluten than is present in normal commercially available bread and consuming 4 slices of the gluten-containing bread will not exceed the amount of gluten that is normally consumed per day (21). The short-term intervention (1 day) with gluten can lead to temporary more symptoms but these should disappear within a few hours after gluten has been eliminated from the diet.

c. Can the primary or secondary mechanism be induced in animals and/or in ex-vivo human cell material?

No, in this study, the effects of gluten-containing bread consumption on gastro-intestinal complaints and wellbeing will be investigated in non-diagnosed gluten-sensitive participants *in vivo* due to the manipulation of expectancy.

d. Selectivity of the mechanism to target tissue in animals and/or human beings Not relevant.

e. Analysis of potential effect

The amount of gluten present in the gluten-containing study bread is at a dose normally present in commercially available bread (i.e. about 4g per slice). The bread is safe for human use and is also safe to consume in this specific (NCGS) study population. Bread is a natural product and has been on the food market for decades where it has a long history of apparent safe use. The short-term intervention (1 day) with gluten can lead to temporary GI symptoms but these should disappear within a few hours after gluten has been eliminated from the diet.

f. Pharmacokinetic considerations

Not relevant.

g. Study population

Volunteers (18-70 years) with self-reported gluten sensitivity (without other GI diseases) will be recruited. In particular, we will screen for coeliac disease and people diagnosed with coeliac disease will be excluded from the study.

h. Interaction with other products

No interaction with other products, posing a health risk to the individual of any kind, are expected.

i. Predictability of effect

Previous studies suggest that a nocebo effect plays a role in the experience of GI symptoms after gluten consumption in individuals with NCGS since a clear basis for underlying biological mechanisms is lacking. Telling self-reported gluten sensitive people that they will be eating gluten-containing study bread containing gluten, is therefore hypothesized to induce (extra)intestinal-symptoms regardless of whether or not the bread actually contains gluten.

j. Can effects be managed?

The risk associated with participating in the intervention is low since the expected side effects are only mild and transient. Moreover, the intervention comprises only 1 day (breakfast and lunch) and the amount of gluten in the gluten-containing bread does not

exceed the amount of gluten in commercially available bread. Participants will be asked to report their symptoms and side effects daily (in the electronic diary). If participants are unable to continue the consumption of the study breads due to intolerable symptoms, they can stop consuming the study breads.

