5.3 Escape medication (if applicable)

We do not expect that the use of escape medication will be necessary. However, participants are permitted to use paracetamol if necessary. The use of nonsteroidal anti-inflammatory drugs (NSAIDs) and opioids are not allowed during the test day. The number of tablets, dose, and the reason for the medication use have to be reported in the electronic diary. If paracetamol does not work adequately and participants experience intolerable symptoms during the study, the involved gastroenterologists in this study ([name]) will advise on whether or not to stop the intervention. In that case, VAS-scores for the remaining questionnaires were replenished using the highest VAS-score achieved thus far.

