7.2 Randomisation, blinding and treatment allocation

After screening and subsequent inclusion in the study, each participant will be assigned to a unique participant identifier code. Participants will be randomly assigned to one of the following experimental conditions:

- 1. Gluten-free expectation and actually receiving gluten-free oat bread (E-, G-).
- 2. Gluten-free expectation but actually receiving gluten-containing oat bread (E-, G+).
- 3. Gluten-containing expectation but actually receiving gluten-free oat bread (E+, G-).
- 4. Gluten-containing expectation and actually receiving gluten-containing oat bread (E+, G+).

The randomisation lists will be generated by an independent co-worker from the same department as the principal investigator who is not further involved in the study, using a publicly available procedure through the internet (http://randomizer.org). This random number generator performs balanced permutations, resulting in an equal number of participants per treatment order followed. Participants will be randomly allocated to the treatment conditions and there will be a stratification on gender using block randomisation (block sizes of 8). The randomisation scheme will be up to n=90, this to be sure in case of dropouts, to randomize potential (new) participants to a new randomization number.

The investigator has no access to the randomisation list that conceals the intervention code. However, since expectation may play a role in the experience of symptoms, the investigator is unblinded to the expectation arm since the investigator has to inform the participant about allocation to the gluten-free or gluten-containing expectation group. Of course, the investigator is blinded to the actual treatment. The randomisation list will be kept in a sealed envelope by the head of the department (prof. dr. [name]), to reveal the treatment in case of medical emergency. Primary investigators of all participating centres will receive the contact details of prof. dr. [name]. The condition numbers as allocated by the independent colleague, who will carry out the randomisation, are registered by the investigator in the screening and enrolment log. Furthermore, the same co-worker will keep the randomisation lists. The "randomization key" will be provided to the investigator only after all experimental and statistical procedures have been completed.

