7.5 Replacement of individual subjects after withdrawal

We do not expect dropouts, because the study is not very burdensome in a physical way and so, is not very difficult to complete. When participants withdrawn from the study after signing informed consent but prior to the test day, or prove to be unsuitable on the basis of the screening and therefore cannot participate in the study, an alternative candidate may be selected, in order to ultimately meet the calculated sample size/power. If participants withdraw from the study before the test day, these results will be destroyed immediately after completion of the study.

When participants withdrawn from the study at the test day (*i.e.* after randomisation), before or after receiving and consuming the study breads because of intolerable symptoms, there will be no replacement of participants. These participants are included in the intention-to-treat analysis, because this is seen as important regarding tolerance of the intervention. In that case, missing VAS-scores for the remaining days of the study period will be imputed with the last observation carried forward.

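### Sections 5.3, 7.5 and 12.1 can score a participant who stops because of intolerable symptoms in up to three ways, so the primary VAS value can depend on the route by which the stop came about

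*Protocol*

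**What the plan says.** Three places in the protocol deal with a participant whose symptoms become intolerable.

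- **Section 5.3 (escape medication).** Paracetamol is optional: "participants are permitted to use paracetamol if necessary". The text continues: "If paracetamol does not work adequately and participants experience intolerable symptoms during the study, the involved gastroenterologists in this study" "will advise on whether or not to stop the intervention". The next sentence says that, in such a case, "VAS-scores for the remaining questionnaires were replenished using the highest VAS-score achieved thus far".
- **Section 7.5 (replacement after withdrawal).** For withdrawal on the test day, "before or after receiving and consuming the study breads because of intolerable symptoms, there will be no replacement of participants". These participants stay in the intention-to-treat analysis, and "missing VAS-scores for the remaining days of the study period will be imputed with the last observation carried forward".
- **Section 12.1, item j (risk analysis).** "If participants are unable to continue the consumption of the study breads due to intolerable symptoms, they can stop consuming the study breads". Paracetamol, advice and scoring are not mentioned, and nothing says that such a participant leaves the study.

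The outcome affected is the primary one: overall GI symptoms on a 0 to 100 mm VAS within 8 hours (section 7.1.1), rated hourly on the test day (section 3.2). On blinding, section 7.2 states that "the investigator is unblinded to the expectation arm since the investigator has to inform the participant about allocation".

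**The concern.** The scoring rule is attached to the way a stop is reached, not to the stop itself. Take two participants who both decline the 12.30 lunch with the same symptoms. One has tried paracetamol and been advised by a gastroenterologist; the remaining scores become the highest value so far. The other simply stops eating the bread and keeps completing the hourly questionnaire; the recorded, possibly falling, scores stand. A third who withdraws altogether may have the last value carried forward.

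This matters for two reasons. First, the trial's hypothesis is that participants told they are eating gluten have more symptoms. If they also stop more often, the choice of rule for stoppers feeds into the expectancy contrast. Second, the route involves some discretion, and the site investigator knows the expectancy arm, which is the factor under test. With 20 participants per group, a few such cases are enough to be visible in a group mean.

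**Working it through.** **Step 1. The rules side by side.**

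- Stop after inadequate paracetamol and gastroenterologist advice (5.3): highest VAS so far, for all remaining questionnaires.
- Withdrawal on the test day because of intolerable symptoms, whoever decides (7.5): last observation carried forward. The wording refers to remaining days, so it is unclear whether it reaches the remaining hours of the test day, which is where the primary outcome lies.
- Bread stopped by the participant, who stays in the study (12.1, item j): no rule stated, so the hourly ratings continue as recorded.

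Section 7.6 provides no follow-up after withdrawal, so recorded scores exist for the third case but not for the second.

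**Step 2. Inputs.** From the protocol: 20 per group and a 15 mm target difference (4.4); the comparison E+G- versus E-G- (section 2), which is 20 versus 20; Expectancy as a between-subjects factor over both breads (9.1), which is 40 versus 40. The protocol gives no figure for the effect of these rules, so there is none to reproduce, and it gives no rate of stopping. The VAS values below are assumptions.

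**Step 3. One participant, value at hour 8.** Assume a peak change of 60 mm and a recorded hour-8 change of 20 mm. The shift in an arm mean is the gap between rules divided by the arm size.

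- 20-person arm: (60 − 20)/20 = 2.0 mm, which is 2.0/15 = 13% of the target.
- Pooled 40-person expectancy arm: (60 − 20)/40 = 1.0 mm, which is 1.0/15 = 7% of the target.

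**Step 4. All three rules on one assumed course.** Baseline 10 mm, eight hourly ratings, bread stopped after the fourth.

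| Rule | Eight ratings (mm) | Mean change | Change at last rating |
|---|---|---|---|
| Highest so far (5.3) | 30, 55, 70, 50, 70, 70, 70, 70 | 485/8 − 10 = 50.6 | 70 − 10 = 60 |
| Last carried forward (7.5) | 30, 55, 70, 50, 50, 50, 50, 50 | 405/8 − 10 = 40.6 | 50 − 10 = 40 |
| As recorded (12.1, item j) | 30, 55, 70, 50, 35, 25, 20, 15 | 300/8 − 10 = 27.5 | 15 − 10 = 5 |

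Shift per participant:

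- Highest so far versus recorded, 20-person arm: (50.6 − 27.5)/20 = 1.2 mm on the post-baseline mean; (60 − 5)/20 = 2.75 mm at the last rating.
- The same, pooled 40-person arm: 23.1/40 = 0.6 mm and 55/40 = 1.4 mm.
- Highest so far versus last carried forward, 20-person arm: (50.6 − 40.6)/20 = 0.5 mm and (60 − 40)/20 = 1.0 mm.

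**Step 5. Which summary applies.** Section 7.1.1 says within 8 hours and section 9.1 uses baseline and after intervention. Neither names hour 8 as the primary time point, so both columns are shown. The effect is smaller on the mean, because the ratings before the stop are common to all rules.

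**The case against.** **Sections 5.3 and 12.1 do not contradict each other on who may stop.** This is right. The gastroenterologists advise, paracetamol is permitted and not required, and section 7.4 lets anyone leave at any time. A reader might infer two rival stopping procedures, but the text does not support that. The defect concerns scoring only.

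**Replacement of scores does not hang on the 5.3 route alone.** Also right: section 7.5 has its own rule. That removes any claim that only one route leads to imputation, but it adds a second rule for a stop with the same cause.

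**The passages can be read in harmony.** The scoring sentence in 5.3 might cover every stop for intolerable symptoms, and its verb might mean filling gaps only, leaving recorded scores alone; 7.5 might concern only the end-of-day questionnaires. These readings are possible, so identical courses can be scored differently but need not be. They do not settle the matter. If 7.5 is limited to later days, someone who withdraws on the test day outside the 5.3 pathway has no stated rule in the primary window. If 5.3 covers all remaining questionnaires, it overlaps with 7.5 on the end-of-day ratings with a different rule.

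**Bias between arms is conjecture.** Largely so. Nothing says that staff escalate more often in E+, and section 3.2 tells participants to contact the researcher if their health changes. A reader might build a case in which two E+ stoppers go through 5.3 and two E- stoppers through 12.1, giving 2 × 40/20 = 4.0 mm, or 27% of 15 mm. That needs a perfect split of routes by arm, which the protocol does not support, and it halves to 2 × 40/40 = 2.0 mm (13%) on the pooled factor. What stands is that knowledge of the arm leaves the route open to influence.

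**Such cases should be rare.** The protocol expects mild, transient symptoms, no need for escape medication and no dropouts. That bears on frequency, but the protocol thought the event likely enough to write rules for it.

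**Conclusion.** The point holds in this form: up to three scoring treatments exist for one event, stopping because of intolerable symptoms, and the primary value can depend on the route. It does not extend to a conflict over who may stop, nor to a demonstrated bias between expectancy arms.

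Under the assumed 60 mm peak and 20 mm recorded change, one affected participant is worth 2.0 mm on a 20-person arm mean and 1.0 mm on a pooled 40-person arm. On the assumed hourly course, the gap between highest-so-far and recorded scores runs from 0.6 mm (pooled arm, post-baseline mean) to 2.75 mm (single group, last rating). The direction, with the highest-score rule giving the larger value, assumes that symptoms ease after the stop, as section 12.1 expects. The total effect depends on how many participants stop and how they divide between arms and routes, which the protocol does not give. This is more than detail left for an analysis plan, because the protocol itself fixes the differing rules. It should be corrected; confidence is moderate because the wording allows milder readings.

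**What to change.** Reconcile sections 5.3, 7.5 and 12.1, item j. No view is taken here on how a stop should be decided or on the use of escape medication.

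State one endpoint rule triggered by the event, namely study bread not fully eaten because of intolerable symptoms, whoever decided:

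- VAS scores recorded after the stop are used as recorded and are not overwritten.
- Only scores that are truly missing are imputed, by one stated rule that explicitly covers both the remaining test-day hours and the later days.
- The other of the two written rules (highest so far, or last carried forward) is applied as a sensitivity analysis.

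Record the slices eaten, the time of the stop and who decided. Paracetamol use is already entered in the diary under 5.3, and questionnaire completion times are already logged under 3.2.

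The cost is wording in three sections, a few eCRF fields and one extra sensitivity analysis. Sample size, visits and participant burden are unchanged.
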